### **8.2 Urine**

During Visit 3 through 4, all voided urine will be collected using standard plastic urine jugs. During visit 3, at each void 1mL of urine will be placed into a labelled cryo tube and the time of voiding will be documented on a table in the CRF. At the completion of Visit 4, all urine will be intermixed and aliquots placed into labelled cryo tubes and frozen at < -60 degrees C in the PI's lab.

### **8.3 Saliva**

During Visit 3-4, three saliva samples will be collected at specific times (**Figure 2**) using absorbent collection devices (e.g. Salivette). They will be centrifuged and the saliva transferred into labelled cryo tubes and frozen at < -60 degrees C in the PI's lab.

## **8.4 Muscle**

At Visit 4, qualified and credentialed study staff (M.D. or PA) will perform a vastus lateralis muscle biopsy of the subject's outer thigh using 1% plain lidocaine for anesthesia. Approximately 100mg of muscle tissue will be obtained using a Bergstrom needle. The tissue will be rinsed with normal saline and flash frozen using liquid nitrogen. The sample will be transferred into a labelled cryo tube and frozen at < -60 degrees C in the PI's lab.

---

## **9.0 Sample and Data Processing**

---

All samples will be processed and analyzed in the PI's lab in the RIOA.

### **9.1 Blood**

Plasma EAA concentrations will be determined by liquid chromatography-mass spectrometry using the internal standard method, as we have done previously (30). Briefly, analytes will be derivatized with 9-fluorenylmethoxycarbonyl and quantification of each peak will be determined using MultiQuant software (version 2.1: AB Sciex).

### **9.2 Urine**

Following ingestion of [15N] alanine, 24-hr dietary nitrogen intake and excretion will be measured. Isotopically labeled nitrogen from the urine samples will be used to determine nitrogen flux according to Fern et al. (24). Whole-body protein synthesis (PS) and breakdown (PB) are calculated from 24-hr urinary urea enrichment according to Stein et al. (25) and used to determine net protein balance and flux. The ingestion of 3MH will increase the naturally-occurring 3MH in the body by less than 5%. This molecule is not reutilized in the body, but only excreted via the urine. Measurement of it in urine will allow determination of muscle protein breakdown.

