## List of Abbreviations

3MH	3-methyl-d3-L-histidine stable isotope
AMDR	acceptable macronutrient distribution range
ANOVA	analysis of variance
AUC	area under the curve
BMI	Body mass index
CRF	Case Report Form
D2O	Deuterated water
DXA	Dual-energy X-ray Absorptiometry
EAA	Essential Amino Acid
GC-MS	Gas chromatograph-mass spectrometry
IRB	Institutional Review Board
MPS	Muscle protein synthesis
NB	Net balance (of protein metabolism)
NHANES	National Health and Nutrition Examination Survey
OPI	Optimal Protein Intake
PS	Whole-body protein synthesis
PB	Whole-body protein breakdown
RDA	Recommended Daily Allowance
RIOA	Reynolds Institute on Aging
UAMS	University of Arkansas for Medical Sciences

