**1.0 Protocol Summary**

This will be a randomized study to demonstrate how animal-based protein-rich food sources can be used by older adults to increase protein intake within pre-existing dietary patterns. In this regard, we propose to augment the current dietary pattern of older Americans by readily available quality protein sources. To this end, we will investigate the effects of recommended and common protein intakes on the maintenance of whole-body protein balance and potential for muscle protein anabolism. Plans to accomplish project goal(s): We will study 3 groups of 10 older subjects during daily protein intakes of 0.8 (recommended dietary allowance [RDA]), 1.1 (National Health and Nutrition Examination Survey [NHANES]), and 1.5 (optimal [OPI]) g/kg/d. Due to common eating patterns in older adults (1), these protein intakes will be structured within 2 meals per day. A 2-day dietary lead-in (matching the subject's intervention paradigm) will proceed each dietary intervention. Whole-body protein balance will be determined during metabolic study days by oral ingestion of 2 grams of the stable isotope N-alanine, and a 24-hr integrated value of muscle protein synthesis will be determined by ingestion of deuterated water. Oral ingestion of 10mg of 3-Methyl-d3-L-histidine and analysis of urine samples will permit measurement of muscle protein breakdown during this period. Integrated post-meal blood EAA will also be determined, as we have demonstrated a relationship between peripheral EAA response and protein anabolism.

Study duration per subject will be about 2 weeks.

---

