**Figure 1:** A greater digestibility requirement (whole-food protein sources) results in a lower stimulation of muscle protein synthesis. These data also demonstrate that greater peripheral EAA are required to increase muscle protein synthesis.

Basing protein distribution optimization upon saturable protein dose studies reflects the “muscle-full” effect theory, which recently was shown to be an artifact of the rapid and transient rise in circulating amino acids rather than a true physiological effect (14). Furthermore, protein recommendations are based upon whole-body protein requirements, not muscle requirements. This is an important consideration as we (15) and others (16) have demonstrated that whole-body protein balance does not plateau with protein intake; i.e., greater improvements in whole-body net protein balance are observed with increasing doses of protein.

The above highlight an incorrect underlying assumption of evenly distributing protein intake throughout the day. More pertinent to the issue is that studies directly testing protein distribution do not provide strong evidence for an even protein distribution being superior to an uneven protein distribution. Despite some promising data (17) in younger adults ( $36.9 \pm 3.1$  years of age), our recent studies (18,19) in older adults (50 – 75 years of age) demonstrated no superior effect of an even protein distribution on whole-body protein balance or muscle protein synthesis over a 24-hour period. More importantly,

our work indicated that total protein intake throughout the day has a direct influence on anabolism (18–21). The take home message from these studies is that total protein intake, not intake patterns, dictates protein homeostasis. This is an important message, as NHANES data indicates that only 17.3% of adults eat more than two meals a day containing  $\geq 30$  grams of protein per meal (1). Thus, the issue becomes one of increasing protein intake in older adults within their pre-existing dietary patterns. Incorporating minimally and further processed meat and poultry products into current dietary patterns provides an easily accessible strategy for older adults to meet higher protein requirements required to maintain protein mass. Therefore, demonstrating the efficacy of these products to meet body protein demands within a preexisting dietary pattern of two meals a day is the focus of this project.

---

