## 5.0 Study Visits

---

Subjects will be required to wear a mask. If they do not have one, a mask will be provided to them by the study staff.

Visit 1: This visit will take place at the UAMS RIOA. At this visit, informed consent discussion will be held. This visit is expected to take less than one hour. If a subject consents, their height and weight will be measured to determine their BMI. Questions will be asked about their medical history and medication use. Eligible, enrolled subjects will be shown a menu of the foods they will be asked to eat to elicit any food allergies or intolerances. If the subject is fasted for 8 hours, has not had caffeine in 12 hours, and has not strenuously exercised in 24 hours, they will undergo body composition testing and DXA scan. If these criteria cannot be met during this visit, subjects will perform these two tests at Visit 2. A blood sample will be drawn for Complete Blood Count (Labcorp). Randomization will occur. Future study visits are scheduled.

[figure not shown]
Visit 2: This visit will occur in a fasted state if the subject did not meet the body composition testing criteria at visit 1. Subjects will undergo body composition testing and DXA scan. Study meals eaten during the 2-day run-in phase will be dispensed. A

10mg dose of 3MH will be provided with instructions to mix it with water, ingest it at 1900, and record the time on the evening prior to study visit 3. Subjects are instructed to eat all of the provided food and add nothing but non-caloric seasonings and condiments. They may have their usual beverages but must not ingest any protein or amino acid supplements during this time. This visit will take place at the UAMS RIOA.

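### Urinary 3MH is read as muscle protein breakdown with no stated handling of the 3MH eaten in meals whose protein dose differs by arm

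*Combined protocol and SAP*

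**What the plan says.** The Protocol Summary (1.0) promises that "analysis of urine samples will permit measurement of muscle protein breakdown during this period", and section 9.2 repeats the claim: "Measurement of it in urine will allow determination of muscle protein breakdown". The compound is labelled; the List of Abbreviations defines 3MH as "3-methyl-d3-L-histidine stable isotope". Under section 5.0 a "10mg dose of 3MH will be provided with instructions to mix it with water, ingest it at 1900" on the evening before Visit 3.

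Section 9.2 justifies the marker by its fate: "This molecule is not reutilized in the body, but only excreted via the urine". The only outside source of 3MH it considers is the tracer itself: "The ingestion of 3MH will increase the naturally-occurring 3MH in the body by less than 5" per cent.

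Section 7.0 sets the arms at 0.8, 1.1 and 1.5 g protein/kg/d. Section 2.1 names the dietary strategy: "Incorporating minimally and further processed meat and poultry products into current dietary patterns". Run-in meals match the arm (1.0, 4.5), and two arm-specific meals are eaten at Visit 3 (5.0), while urine is being collected.

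Section 8.2 keeps a 1 mL aliquot of each Visit 3 void, with its time. It then says: "At the completion of Visit 4, all urine will be intermixed and aliquots placed into labelled cryo tubes". The documents give no equation from 3MH to breakdown, no meal assay and no dietary correction.

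**The concern.** A marker of the subject's own muscle breakdown works only if its other sources are absent, equal between arms or removed. Here a likely other source is part of the intervention. Meat and poultry are muscle. On the protocol's premise that 3MH reports on muscle protein, is not reused and leaves only in urine, 3MH absorbed from those foods would take the same route out.

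If the amount eaten rises with the randomised dose, the error is differential between arms. Neither randomisation nor a larger sample removes it. Unchanged breakdown could look as if it rose with protein intake, and a real fall could be hidden or reversed. Subjects take a dedicated tracer dose for this measure, so it should be interpretable.

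**Working it through.** The plan states no figure for this measure, so there is none to reproduce. The check has two parts.

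**1. What the label can and cannot do**

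Let E be unlabelled 3MH from the subject's muscle and D unlabelled 3MH from food, both per day.

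- Excretion: unlabelled output = E + D.
- Tracer dilution: the labelled-to-unlabelled ratio depends on total unlabelled 3MH, so it also reflects E + D.
- Decay constant: with steady linear kinetics, pool = (E + D)/k. The constant k does not change with D, but turning k into an amount needs the pool, and k × pool = E + D again.

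A method resting on k alone would be less affected near steady state. Two meals inside the collection period are not a steady state, and the plan does not say that such a method is used.

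**2. Possible size**

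Inputs:
- Doses of 0.8, 1.1 and 1.5 g/kg/d (section 7.0). Section 4.5 gives 1 as its example for the middle arm; the OPI/RDA comparison does not depend on this.
- Assumption: dietary 3MH is proportional to protein dose, that is, a constant meat share.
- Assumption: d = D/E in the RDA arm. The documents do not give d, so a range is shown.
- No true difference in E between arms.

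Dietary 3MH relative to RDA is 1.1/0.8 = 1.375 in NHANES and 1.5/0.8 = 1.875 in OPI. Then

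apparent ratio to RDA = (1 + d × dose/0.8)/(1 + d).

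| d | NHANES vs RDA | OPI vs RDA |
|---|---|---|
| 0.05 | 1.06875/1.05 = +1.8% | 1.09375/1.05 = +4.2% |
| 0.10 | 1.1375/1.10 = +3.4% | 1.1875/1.10 = +8.0% |
| 0.25 | 1.34375/1.25 = +7.5% | 1.46875/1.25 = +17.5% |
| 0.50 | 1.6875/1.50 = +12.5% | 1.9375/1.50 = +29.2% |
| 1.00 | 2.375/2.00 = +18.8% | 2.875/2.00 = +43.8% |

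For masking, suppose true breakdown in OPI is t times that in RDA. The arms look equal when t + 1.875d = 1 + d, so t = 1 − 0.875d. At d = 0.10 a true fall of 8.75% would be hidden; at d = 0.25, a fall of 21.9%.

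Under proportionality the direction is upward for every d above zero. The gradient is steeper if the extra protein in the higher arms is mainly meat, and shallower if it is mainly eggs or dairy.

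**The case against.** The strongest reply is that the tracer is labelled and the equation is not given, so an additive model of total 3MH may not be the planned calculation. Part of this stands. The percentages illustrate one plausible model and do not predict the trial's bias. The label alone is still no answer, because food 3MH and muscle 3MH are both unlabelled.

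A second reply is that the documents never say that meat contains 3MH, nor what share of each arm's protein is meat. That is correct. The presence of 3MH in meat is inferred from the protocol's own premise and its choice of foods, and the size stays open.

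A reader might also infer four stronger points that the documents do not support:

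- **That the main results are compromised.** The hypothesis (3.0) concerns muscle protein synthesis and whole-body balance, measured with D2O and 15N-alanine. Neither uses 3MH.
- **That the plan tests 3MH breakdown between arms.** The ANOVA list in 10.1 includes breakdown, but the wording reads as the whole-body value; 3MH is not named.
- **That only pooled urine survives.** Section 8.2 keeps timed aliquots from Visit 3, and subjects arrive fasted for 10 hours or more, so any void before the first meal is available separately. The Figure 2 timeline is not shown, so the full schedule cannot be judged.
- **That a fasted Visit 4 void would solve the problem.** It follows an arm-specific afternoon or evening meal, so carry-over could still track dose.

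**Conclusion.** The concern holds in a limited form. As written, the plan would label as muscle breakdown a quantity that can include 3MH from food, and the food differs by randomised arm. Any estimate based on excretion, appearance or dilution is biased upward with dose if the meals' 3MH rises with dose. The bias vanishes only if the meals carry no 3MH, carry the same amount in every arm, or are corrected for.

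The illustrative size is 4% to 44% for OPI over RDA and 2% to 19% for NHANES over RDA, with no true difference. Both ranges rest on the additive model, on proportionality to dose, and on an assumed dietary share of 5% to 100% of endogenous output in the RDA arm. The consequence is confined to one ancillary measure for which no between-arm test is explicitly listed. It should be corrected before the 3MH data are analysed, and it does not put the hypothesised outcomes in doubt.

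**What to change.** In section 9.2:

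1. State the equation that turns urinary 3MH into muscle protein breakdown. Base it on the timed Visit 3 void aliquots already kept, using the labelled-to-unlabelled ratio.
2. Assay 3MH in a sample of each arm's meals and subtract the amount each subject ate. State the absorption assumed.
3. Use voids before the first Visit 3 meal as a sensitivity analysis, and acknowledge possible carry-over from the arm-matched run-in meals.

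In section 10.1, say whether 3MH breakdown is compared between arms or is descriptive only.

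If the meals are not assayed, report the result as total 3MH (dietary plus endogenous), descriptively, with no between-arm conclusion on muscle breakdown.

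The cost is a few assays on meal samples, or giving up that one conclusion. No dose, menu or visit needs to change.

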### **9.3 Saliva**

Body water enrichments following D2O ingestion will be determined through isotope exchange with acetone using GC-MS (29).

### **9.4 Muscle**

MPS will be determined by oral D2O ingestion to assess 24-hr muscle protein synthesis using the single biopsy approach (26). In the interest of brevity, the sample preparation methods are standard in the PI's laboratory and have recently been outlined in detail (27). Muscle preparations will be analyzed for incorporation of deuterated alanine by GC-MS using partial integration (28). The daily rate of muscle protein synthesis will be determined according to Gasier et al. (27).

### **9.5 Dual Energy-Xray Absorptiometry**

This test will be used to measure body composition (fat mass, lean mass, and percent body fat). Subjects will be asked to remove all metal, thick clothing, and heavy plastic which could interfere with the DXA scans. The subject's ID, age, ethnicity, height and weight will be entered into the computer prior to the scanning. The subject will be asked to lie down on the DXA table in the supine position. The participant will be centered on the table within the scanning area. The subject's shoulders and hips will be centered, and the hands will be placed by the side of the legs in a pronated position. Subjects will be instructed to remain still for the duration of the full-body scan. A trained DXA technician will perform and analyze all scans. Subjects will be asked to fast for 8 hours, avoid caffeine and alcohol for 12 hours, and avoid strenuous exercise for 24 hours prior to this procedure.

### **9.6 Multi-frequency Bioelectrical Impedance Analysis**

This test will measure total body and segmental water, to be combined with the DXA measures for a more accurate body composition estimates. To obtain measurements, subjects are asked to stand barefoot on a calibrated scale to obtain subject weight. Once subject height, sex, and age are entered into the device, subjects are instructed to

hold onto two handles and remain still while an imperceptible electrical current runs between electrodes in the handles and scale. Total assessment time is <2 minutes. Subjects will be asked to fast for 8 hours, avoid caffeine and alcohol for 12 hours, and avoid strenuous exercise for 24 hours prior to this procedure.

---

## **10.0 Statistical Analysis – Data Use**

---

### **10.1 Statistical Analysis**

Means by which experimental data will be analyzed or interpreted: Changes in whole-body protein synthesis, breakdown, flux, net balance, muscle protein synthesis, and plasma EAA area under the curve (AUC) between groups will be assessed with a one-way analysis of variance (ANOVA). In the event of a main effect of group, appropriate post-hoc comparisons will be carried out. Statistical significance will be accepted at an alpha level of  $p \leq 0.05$ .

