## 7.0 Randomization

---

Subjects will be randomized equally to one of three groups after they are determined to be eligible using a generated list of group designations that corresponds to subject ID. Efforts will be made to balance the sexes within each group. The three groups utilized are:

- 1) recommended dietary allowance for protein (RDA; 0.8g/kg/day);
- 2) habitual protein intake consistent with population level norms (NHANES; 1.1g/kg/day);
- 3) optimal protein intake (OPI; 1.5g/kg/day).

---

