#### **10.5 Power Calculations**

We propose a group size of 10 per group, based upon an ANOVA model to compare the nutrition interventions. With this sample size, the ANOVA model has 80% power to detect effect sizes of  $f = 0.484$  or larger. This estimate assumes that the basal covariate explains 50% of the variation in the response and a 5%  $\alpha$ -level is used to determine statistical significance.

---

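### Section 10.1 plans an unadjusted ANOVA while section 10.5 sizes the trial on an unnamed covariate; pre-diet lean mass and sex are recorded but used in no analysis, and f = 0.484 does not reproduce at 10 per group

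*Combined protocol and SAP*

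**What the plan says.** **Analysis (10.1).** Six outcomes are listed: whole-body protein synthesis, breakdown, flux and net balance, muscle protein synthesis, and plasma EAA AUC. Group differences "between groups will be assessed with a one-way analysis of variance (ANOVA", with post-hoc comparisons after a significant group effect. The threshold for significance is p ≤ 0.05. No covariate appears.

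**Sample size (10.5).** Ten subjects per arm are planned, and the smallest effect said to be detectable with 80% power is f = 0.484. On the covariate behind that figure the section states: "This estimate assumes that the basal covariate explains 50% of the variation in the response". That covariate is not named here or elsewhere.

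**Variables known before the diets start.** Section 9.5 says of DXA: "This test will be used to measure body composition (fat mass, lean mass, and percent body fat". Section 5.0 and the study calendar place it at Visit 1 or Visit 2, before the run-in meals are eaten. Allocation is 1:1:1 once eligibility is established, and on sex section 7.0 adds: "Efforts will be made to balance the sexes within each group". No analysis uses lean mass or sex.

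**Timing of the outcomes.** The isotope procedure runs from Visit 3 to Visit 4, after a run-in diet that already follows the allocated group (4.5, 5.0). The only biopsy is at Visit 4 (8.4), and muscle protein synthesis uses a single-biopsy method (9.4).

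**The concern.** The sample size relies on an adjustment that the analysis does not make. Nor is it clear what the covariate could be. The usual meaning would be each subject's own pre-intervention value of the outcome, and the documents describe no such measurement for the kinetic outcomes.

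With 30 completers and 27 error degrees of freedom, between-subject variation largely decides whether the hypothesized ordering RDA < NHANES < OPI can be seen. If lean mass or sex explains a worthwhile share of it, leaving them out keeps that share in the error term. Where allocation succeeds in balancing sex, omitting sex also makes the F test conservative: its variance no longer contributes to chance differences between groups but still sits in the error. Choosing covariates after 30 results are known would invite selective reporting, so the choice belongs in the plan.

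**Working it through.** **Inputs.** From 10.5: 10 per group in three groups (N = 30), f = 0.484, 80% power, R² = 0.50 for the basal covariate. From 10.1 and 10.5: α = 0.05. The R² of lean mass and sex with the outcomes is not given, so 0 to 0.5 is an assumed range.

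**Formula.** Power = P(F′ > F crit), where F′ is noncentral F with 2 and 30 − 3 − c degrees of freedom, c is the number of covariates, and λ = N f² / (1 − R²). Here f is on the scale of the unadjusted within-group SD.

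**Step 1: the plan's own figure.** With c = 1 and R² = 0.5, λ = 30 × 0.484² / 0.5 = 14.06 on 2 and 26 df. Power is 89.6%, not 80%, and f detectable at 80% power is 0.425.

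Other readings at 10 per group also miss 0.484:
- f on the residual-SD scale: 0.601
- 50% read as a correlation (R² = 0.25): 0.520
- 90% power: 0.487; 85% power: 0.453
- two groups: 0.470; four groups: 0.391

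The stated value would need R² of about 0.35 at this size. It is matched by 8 per group with one covariate at R² = 0.5: N = 24, λ = 24 × 0.484² / 0.5 = 11.24, 2 and 20 df, power 80.0%, detectable f = 0.4838.

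**Step 2: the test as written in 10.1.** With c = 0, λ = 30 × 0.484² = 7.03 on 2 and 27 df. Power is 60.5%. Detectable f at 80% is 0.600. At f = 0.484, 80% power would need about 15 per group (80.7%).

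**Step 3: two covariates (lean mass and sex), 2 and 25 df.** The formula above assumes covariates exactly balanced across groups, which 10 per arm will not deliver. On average, chance imbalance inflates the variance by 1 + 2/(27 − 2 − 1) = 1.083, so detectable f rises by √1.083 = 1.041. In the imbalance power column, the lower figure uses this factor. The upper figure averages over random draws of lean mass with sex exactly balanced in every arm and equally spaced group means.

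| Assumed R² | Power at 0.484, no imbalance | Power at 0.484, with imbalance | Detectable f, no imbalance | Detectable f × 1.041 |
|---|---|---|---|---|
| 0 | 60.1% | 56.5–58.4% | 0.602 | 0.627 |
| 0.1 | 65.0% | 61.3–63.3% | 0.572 | 0.595 |
| 0.3 | 76.5% | 72.9–74.9% | 0.504 | 0.525 |
| 0.5 | 89.4% | 86.8–88.2% | 0.426 | 0.443 |

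**Step 4: gain, loss and break-even against 60.5% unadjusted.**
- R² = 0: a loss of 60.5 − 58.4 = 2.1 to 60.5 − 56.5 = 4.0 points.
- R² = 0.3: a gain of 12.4 to 14.4 points.
- R² = 0.5: a gain of 26.3 to 27.7 points.
- Break-even R² is about 4.5% to 8.5%. Counting only the two lost degrees of freedom would give 0.9%, which is too favourable.

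**The case against.** An unadjusted ANOVA in a randomized trial is valid: it brings no bias and no inflation of type I error. A reader might infer that the planned test is wrong in that sense. The documents do not support that reading, and the issue is power and consistency.

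A reader might also infer that the trial is certainly discarding precision. That does not follow. No R² is given for lean mass or sex with any outcome, and the 50% in 10.5 belongs to an unnamed covariate and cannot be transferred to these two. Sex and lean mass overlap, so the second may add little. Outcome units are not stated. Lean mass is easier to justify for whole-body kinetics, with intake dosed per kg and BMI allowed up to 35, than for muscle protein synthesis or EAA AUC. Section 7.0 promises only efforts at sex balance and describes no stratification, so the argument from matching analysis to allocation is modest. Adjustment is not free either, as Step 4 shows. All of this stands, and it makes the gain conditional.

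One could reply that 10.5 shows the sponsor already intends to adjust. If so, 10.1 should say so and name the covariate. A sample taken on the morning of Visit 3 would not be a pre-diet value, because the group-specific run-in has by then been eaten.

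Two further limits apply. The point covers the outcomes listed in 10.1. Muscle protein breakdown from 3MH (9.2) is not among them and has no stated test. The match to 8 per group is numerical only: the documents do not say that the calculation was run at that size.

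**Conclusion.** The point holds as a mismatch between 10.1 and 10.5, together with a missed opportunity of unknown size. The analysis as written has about 60% power at the stated effect, and the stated effect does not follow from the stated inputs. These two results need only the plan's own figures and the noncentral F.

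The benefit of adjusting for lean mass and sex rests on an assumed R². It is worthwhile at 0.3 or above, close to nil at about 0.1, and slightly negative below the break-even. Since 10.5 already relies on a covariate explaining half the variance, and since the downside is only a few points, pre-specified adjustment is a reasonable choice. The plan should be changed, although the unadjusted test would not invalidate the trial.

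**What to change.** **In 10.1:** pre-specify an ANCOVA with group and sex as factors and pre-diet DXA lean mass as covariate, using lean mass divided by body weight for outcomes expressed per kg. State the units and the covariate for each outcome, with a reason where the link is less obvious (muscle protein synthesis, EAA AUC). Report adjusted group means and contrasts with 95% confidence intervals. Keep the unadjusted one-way ANOVA as a sensitivity analysis.

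**In 10.5:** replace the basal covariate with these named covariates and restate detectable f at 10 per group and 80% power. The values are 0.600 with no covariate and, with two covariates, 0.602 at R² = 0, 0.572 at 0.1, 0.504 at 0.3 and 0.426 at 0.5. Note that these rise by about 4% once chance imbalance is allowed for. Label the R² values as assumptions, and correct or explain 0.484.

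**Cost:** wording in two sections, settled before outcome data are seen. No new measurements or visits are needed. The statistical price is two error degrees of freedom plus chance imbalance, about 2 to 4 points of power if the covariates explain nothing.
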